**U.S. Requirements**

Clinical trial documents must be retained by the investigational site for a period of 2 years after the latter of the following dates (812.140(d)):

- The date on which the investigation is terminated or completed
- the date the records are no longer required for purposes of supporting an application to the FDA to market the device

All documents must be made available for monitoring or auditing by Coherex Medical’s representative or representatives of the FDA and other applicable regulatory agencies. The Investigator must ensure the availability of source documents from which the information on the case report forms was derived.

**17. AMENDMENTS TO CLINICAL INVESTIGATIONAL PLAN**

Trial related documents such as, the Investigator Brochure (IB), Report of Prior Investigations (RPI) CIP, CRFs, Informed Consent form and other subject information, or other clinical trial

	Title: The WAVECREST 2 Trial  Clinical Investigational Plan	Doc. #: CHX_IP014	Rev: H
---	--	-----------------------------	------------------

documents will be amended as needed throughout the clinical trial, and a justification statement will be included with each amended section of a document. Proposed amendments to the CIP will be agreed upon between the Sponsor and the Co-Principal Investigators.

The amendments to the CIP and the subject’s Informed Consent will be notified to, or approved by, the IRB/EC and regulatory authorities, if required. The version number and date of amendments will be documented.

The amendment will identify the changes made, the reason for the changes and if it is mandatory or optional to implement the amendment.

Any amendment affecting the subject requires that the subject be informed of the changes and a new consent be signed and dated by the Investigator at the subject’s next follow-up.

Changes to, or formal clarifications of, the CIP will be documented in writing and provided to the Investigators. This information will be incorporated when an amendment occurs.

**18. TRIAL COMMITTEES**

**18.1 Physician Advisory Committee**

A Physician Advisory Committee, consisting of physicians of varying specialties (interventional cardiology, electrophysiology, neurology) and a Sponsor representative, will be responsible for oversight of the scientific and operational aspects, and reporting of trial results. [REDACTED]

[REDACTED] he committee will meet as needed to review trial progress and may advise the Sponsor on potential trial modifications during the trial conduct phase. The committee will advise the Sponsor on actions to be taken upon recommendations from the Data Monitoring Committee (DMC). The Physician Advisory Committee will also make recommendations regarding any publications arising from data generated from the trial.

**18.2 Clinical Event Committee (CEC)**

A Clinical Events Committee (CEC) composed of physicians from different specialties will be appointed by the Sponsor to adjudicate primary effectiveness and safety endpoints, secondary endpoints, death (cardiovascular vs. non-cardiovascular), and bleeding categories. CEC members will not be on the Physician Advisory Committee or Investigators in the trial. The CEC will be composed of at least 4 physicians: 2 stroke Neurologists and 2 Cardiologists. Each CEC meeting will require a quorum. The names of the CEC members, responsibilities of the CEC, the frequency of CEC meetings, the adjudication process and the process for documentation of the adjudication outcome will be specified in a **CEC Charter**. CEC members will be blinded to subject’s randomization assignment and implanted device.

**18.3 Data Monitoring Committee (DMC)**

A Data Monitoring Committee (DMC) will be appointed by the Sponsor to review on a regular basis accumulating data from the trial. The DMC will advise the Sponsor regarding the continuing safety of trial subjects and those yet to be recruited to the trial, as well as the continuing validity and scientific merit of the trial and evaluate results from interim analyses to

	Title: The WAVECREST 2 Trial  Clinical Investigational Plan	Doc. #: CHX_IP014	Rev: H
---	--	-----------------------------	------------------

provide recommendations to the Sponsor on stopping enrollment and declaring early success. Based on accumulating data from the trial, the DMC will recommend whether to continue, suspend, modify or stop the trial. The DMC will be composed of at a minimum one statistician and 2 physicians. The composition, responsibilities, frequency of DMC meetings, handling of emergency situations and documentation of DMC meetings will be specified in a **DMC Charter**.

## 19. OUTSOURCING OF DUTIES AND FUNCTIONS

The Sponsor may transfer any or all of the duties and functions related to the clinical trial, including monitoring, to an external organization (such as a CRO or individual contractor), but the ultimate responsibility for the quality and integrity of the clinical trial will reside with the Sponsor. All requirements applying to the Sponsor will also apply to the external organization inasmuch as this organization assumes the clinical trial related duties and functions of the Sponsor.

### 19.1 Echocardiography Core Lab

An Echocardiography Core Laboratory (ECL) will be appointed by the Sponsor to assess TEEs for LAA closure and presence of device thrombus and TTEs for pericardial effusion post-procedure. The ECL will also assess post-stroke TEEs to ascertain the mechanism of stroke. The ECL will provide an ***Echocardiography Protocol*** and training to investigational sites. The responsibilities and processes to be followed by the ECL will be described in an ***ECL Manual of Operations***.

## 20. INVESTIGATION SUSPENSION OR TERMINATION

### 20.1 Premature trial termination

The Sponsor reserves the right to stop the trial at any stage, with appropriate written notice to the Investigator.

Possible reasons for early termination of the trial by the Sponsor, either at local, national or international level, may include, but are not limited to:

- The device / therapy fails to perform as intended
- Occurrence of USADE which cannot be prevented in future cases
- Sponsor’s decision
- Recommendation from DMC to Physician Advisory Committee and Sponsor
- Request from Regulatory bodies
- Request of Ethics Committee(s)
- Concern for subject safety and welfare
- Failure to secure subject Informed Consent prior to any investigational activity
- Failure to report unanticipated adverse device effects within 10 working days to Sponsor and the EC, as required
- Repeated non-compliance with this CIP or the Clinical Trial Agreement
- Inability to successfully implement this CIP
- Violation of the Declaration of Helsinki 2008

	Title: The WAVECREST 2 Trial  Clinical Investigational Plan	Doc. #: CHX_IP014	Rev: H
---	--	-----------------------------	------------------

- Violation of applicable national or local laws and regulations
- Falsification of data, or any other breach of ethics or scientific principles
- Loss of or unaccounted use of investigational device inventory

The trial will be terminated according to applicable regulations.

The Investigator may also discontinue participation in the clinical trial with appropriate written notice to the Sponsor.

Should either of these events occur, the Investigator will return all documents to the Sponsor; provide a written statement as to why the premature termination has taken place and notify the IRB/EC and/or the Competent Authority (if applicable). Follow-up for all enrolled subjects will be as per CIP requirements.

An Investigator, IRB/EC or regulatory authority may suspend or prematurely terminate participation in a clinical trial at the investigational sites for which they are responsible.

If suspicion of an unacceptable risk to subjects arises during the clinical trial or when so instructed by the IRB/EC or regulatory authority, Coherex Medical may suspend the clinical trial as appropriate while the risk is assessed. Coherex Medical will terminate the clinical trial if an unacceptable risk is confirmed.

Coherex Medical will consider terminating or suspending the participation of a particular investigational site or Investigator in the clinical trial if monitoring or auditing identifies serious or repeated deviations on the part of an Investigator.

If suspension or premature termination occurs, the terminating party will justify its decision in writing and promptly inform the other parties with whom they are in direct communication. The Investigator and Coherex Medical will keep each other informed of any communication received from IRB/EC or regulatory authority.

If for any reason Coherex Medical suspends or prematurely terminates the trial at an individual investigational site, Coherex Medical will inform the responsible regulatory authority, as appropriate, and ensure that the IRB/EC are notified, either by the Investigator or by Coherex Medical. If the suspension or premature termination was in the interest of safety, Coherex Medical will inform all other Investigators.

If suspension or premature termination occurs, Coherex Medical will remain responsible for providing resources to fulfill the obligations from the CIP and existing agreements for following up the subjects enrolled in the clinical trial, and the Investigator or authorized designee will promptly inform the enrolled subjects at his/her investigational site, if appropriate.

## 20.2 Resuming the trial after temporary suspension

When Coherex Medical concludes an analysis of the reasons for the suspension, implements the necessary corrective actions, and decides to lift the temporary suspension, Coherex Medical will inform the Investigators, IRB/EC, or regulatory authority, where appropriate, of the rationale, providing them with the relevant data supporting this decision.

	Title: The WAVECREST 2 Trial  Clinical Investigational Plan	Doc. #: CHX_IP014	Rev: H
---	--	-----------------------------	------------------

Concurrence will be obtained before the clinical trial resumes from the IRB/EC or regulatory authority where appropriate.

If subjects have been informed of the suspension, the Investigator or authorized designee will inform them of the reasons for resumption.

### 20.3 Trial conclusion

The trial will be concluded when:

- All sites are closed AND
- The Final Report generated by Coherex Medical or Coherex Medical has provided formal documentation of trial closure

## 21. TRAINING

### 21.1 Training of Investigators and Trial Personnel

Investigators and trial personnel who will be responsible for day-to-day activities for the trial must have completed GCP training per the sites standard operating procedures. Sponsor will provide training on the WAVECREST 2 CIP and the eCRF database.

Additionally, Sponsor will provide training on WaveCrest device IFU to implanting physicians and imaging training for the implant procedure to echocardiographers assigned to the trial.

Sponsor training on the WaveCrest implant procedure will include:

- an on-line self-study simulation module which will present device and procedure steps,
- training presentation focusing on anatomical considerations, device details and required procedural steps, and
- Table-top training with model to simulate implant procedure steps.

[figure not shown]
Certification of implanting Investigators will be based on a competency assessment. On-site case support will be provided by the Sponsor for all implant procedures. Prior to each procedure, a review of baseline imaging studies may be conducted by one of Sponsor's certified clinical trainer with the Investigator.

The echocardiographer will receive imaging training for the implant procedure from the Sponsor. The Sponsor will provide training to echocardiographers on the **Echocardiography Protocol**.

A record of training activities and the completed training process will be kept in a **Training Log** provided by the Sponsor.

Table 8 describes the training modules required for the specific roles for trial personnel (Investigator, trial coordinator, echocardiographer and blinded trial personnel who will administer the QVSFS) assigned to the trial:

	Title: The WAVECREST 2 Trial  Clinical Investigational Plan	Doc. #: CHX_IP014	Rev: H
---	--	-----------------------------	------------------

**22. PUBLICATION POLICY**

[figure not shown]
Results of this clinical trial will be submitted for publication without regard for whether the trial results are positive or negative. The Physician Advisory Committee will be responsible for oversight of the publication process. The Physician Advisory Committee (or a Publication Committee appointed by the Sponsor and Physician Advisory Committee) will have oversight of publications of results of the trial. Site-specific clinical trial results may be published by Investigators in compliance with the Clinical Trial Agreement.

For more information on publication guidelines, please refer to the International Committee of Medical Journal Editors (ICMJE) on [www.icmje.org](http://www.icmje.org).

This trial will be posted on ClinicalTrials.gov and results will be posted on ClinicalTrials.gov as required.

Upon receiving IDE approval from the FDA, this clinical trial will be registered on ClinicalTrials.gov. A full report of the pre-specified outcomes, including any negative outcomes, will be made public through the ClinicalTrials.gov website no later than 12 months after trial completion, as required by Section 801 of the FDA Amendments Act. If this clinical trial is terminated early, the Sponsor will make every effort to hasten the release of the pre-specified outcomes through the ClinicalTrials.gov website.

 	Title:  The WAVECREST 2 Trial Clinical Investigational Plan	Doc. #:  CHX_IP014	Rev:  H
--	---	---------------------------------	----------------------

## APPENDIX I: Acronyms and Definitions

### ACRONYMS

AF	Atrial Fibrillation
CAS	Carotid artery surgery
CBC	Complete Blood Cell
CEA	Carotid endarterectomy
CEC	Clinical Events Committee
CT	Computed tomography
DMC	Data Monitoring Committee
EC	Ethics Committee
ECL	Echocardiography Core Lab
eCRF	Electronic Case Report Form
ePTFE	Expanded polytetrafluoroethylene
GI	Gastrointestinal
HGB	Hemoglobin
HIPAA	Health Insurance Portability and Accountability Act
IDE	Investigational Device Exemption
INR	International Normalized Ratio
IRB	Institutional Review Board
IV	Intravenous
LAA	Left Atrial Appendage
MRI	Magnetic Resonance Imaging
mRS	Modified Rankin Scale
NIH	National Institutes of Health
OAC	Oral Anticoagulant – synonymous with “anticoagulant”
NYHA	New York Heart Association
QVSFS	Questionnaire for Verifying Stroke-Free Status
TEE	Transesophageal Echocardiogram
TIA	Transient Ischemic Attack
TTE	Transthoracic Echocardiogram
WBC	White Blood Cell

	Title: The WAVECREST 2 Trial  Clinical Investigational Plan	Doc. #: CHX_IP014	Rev: H
---	--	-----------------------------	------------------

### DEFINITIONS

Anticoagulant	Medication used to reduce thrombogenic properties of blood regardless of mechanism or action (Abbreviated OAC)
Antiplatelet	Medication used to inhibit platelet aggregation (P2Y12 inhibitor; aspirin)
Atrial Fibrillation	
Paroxysmal	
 
• AF that terminates spontaneously or with intervention within 7 days of onset.
 
• Episodes may recur with variable frequency.
 

Persistent	
 
• Continuous AF that is sustained > 7 days and < 12 months
 

Long-Standing Persistent	
 
• Continuous AF that is sustained > 12 months
 

Permanent	
 
• Continuous AF that is sustained > 12 months that cannot or is not planned to be resolved with treatment
 
• Note: For the purpose of this CIP, and for comparison to earlier LAA occlusion studies, permanent AF includes any subject with sustained AF ≥2 months without regard to ongoing treatment status.
 

Cardiac Tamponade	
Compression of the heart by an accumulation of fluid or air in the pericardial sac (i.e., Pericardial Effusion). Cardiac tamponade may range from asymptomatic to life-threatening in severity and may include one or more of the following characteristics:
 
 
• Hypotension, jugular venous distension, and/or muffled heart sounds
 
• Chest pain, palpitations, shortness of breath, or in more severe cases, dizziness, syncope and altered mental status
 
• Pulseless electrical activity cardiac arrest
 
• Pulsus paradoxus (decrease in systolic blood pressure >10 mm Hg with inspiration)
 
• Sinus tachycardia, low voltage, or electrical alternans on ECG
 
• Enlarged cardiac silhouette on chest X-ray
 
• Echocardiographic findings including pericardial effusion, right ventricular diastolic collapse, right atrial systolic collapse, hepatic veins indicating elevated systemic venous pressure, reduced left ventricular end-diastolic and end-systolic dimensions, reduced stroke volume & cardiac output, inspiratory bulge/bounce of the interventricular septum into the left ventricle, abnormal respiratory changes in Doppler flow velocity, and plethoric IVC
 
• Requiring interventional or surgical drainage
 

Clinical Trial/ Clinical Study	For purposes of this trial and all related documents (i.e., Informed Consent, Clinical Trial Agreement, etc.) the terms trial and study are used interchangeably.
Device Duration	Time from introduction of delivery sheath to removal of delivery sheath
Left Atrial Duration	Time from transseptal puncture to removal of delivery sheath
Device Embolization	A device that has migrated from the Left Atrial Appendage to a different cardiovascular structure.
Device Migration	A device that has shifted from its original position to a different position in the Left Atrial Appendage post-

	Title: <h2 style="text-align: center;">The WAVECREST 2 Trial Clinical Investigational Plan</h2>	Doc. #: CHX_IP014	Rev: H
---	---	-----------------------------	------------------

Myocardial Infarction 3rd Universal Definition (see Thygesen, et al. Circulation. 2012;126:2020-2035 for additional details)	Acute Myocardial Infarction (AMI) - Evidence of myocardial necrosis consistent with acute myocardial ischemia. Any one of the following meets MI diagnosis: 
 
• Detection of a rise and/or fall of cardiac biomarker values [preferably cardiac troponin (cTn)] with at least one value above the 99th percentile upper reference level (URL) and with at least one of the following:               
 
○ Symptoms of ischemia
 
○ New/presumed new significant ST-segment-T wave (ST-T) changes or new LBBB
 
○ Development of pathological Q waves in ECG
 
○ Imaging evidence of new loss of viable myocardium or new regional wall motion abnormality
 
○ Identification of an intracoronary thrombus by angiography or autopsy
 
 
 
• Cardiac Death with symptoms suggestive of myocardial ischemia and presumed new ischemic ECG changes or new LBBB, but death occurred before cardiac biomarkers were obtained, or before cardiac biomarker values would be increased
 
• For PCI-related MI or Prior MI – please see Thygesen, et al.
 

Procedure Duration	Time from venous puncture to removal of delivery catheter
Technical Success	
 
• Occlusion of the LAA
 
• No device-related complications
 
• No leak >5mm on color Doppler TEE
 

Procedural Success	
 
• Technical success
 
• No procedure-related complications except uncomplicated (minor) device embolization (resolved by percutaneous retrieval during the procedure without surgical intervention or damage to surrounding cardiovascular structures)
 

Device Success	
 
• Device deployed and implanted in the correct position
 

Death	VARC II Definition 
Cardiovascular Death	Death that meets any of the following criteria: 
 
• Death due to proximate cardiac cause (e.g., myocardial infarction, cardiac tamponade, worsening heart failure)
 
• Death caused by non-coronary vascular conditions such as neurological events, pulmonary embolism, ruptured aortic aneurysm, dissecting aneurysm, or other vascular disease
 
• Procedure-related death, including death related to complication of the procedure or treatment for a complication of the procedure
 
• Valve-related death including structural or non-structural valve dysfunction or other valve-related adverse events
 
• Sudden or unwitnessed death
 
• Death of unknown cause
 

Non-cardiovascular Death	Death in which the primary cause of death is clearly related to another condition (e.g., trauma, cancer, suicide)
Endocarditis	Fulfillment of the Duke endocarditis criteria  (see http://www.medcalc.com/endocarditis.html )
LAA Closure	No residual leak or if leak is present, residual gap ≤ 5mm (assessed by the ECL)
Major Bleeding	Bleeding Academic Research Consortium (BARC)  definition
Type 3a	Overt bleeding plus hemoglobin drop of 3 to < 5g/dL* (provided hemoglobin drop is related to bleed) Any transfusion with overt bleeding

	Title: The WAVECREST 2 Trial  Clinical Investigational Plan	Doc. #: CHX_IP014	Rev: H
---	--	-----------------------------	------------------

Type 3b	Overt bleeding plus hemoglobin drop $\geq 5\text{g/dL}^*$ (provided hemoglobin drop is related to bleed) Cardiac tamponade Bleeding requiring surgical intervention for control (excluding dental/nasal/skin/hemorrhoid) Bleeding requiring intravenous vasoactive agents
Type 3c	Intracranial hemorrhage (does not include microbleeds or hemorrhagic transformation, does include intraspinal) Subcategories confirmed by autopsy or imaging or lumbar puncture Intraocular bleed compromising vision
Type 4	CABG-related bleeding - Perioperative intracranial bleeding within 48 h Reoperation after closure of sternotomy for the purpose of controlling bleeding Transfusion of $\geq 5$ U whole blood or packed red blood cells within a 48-h period† Chest tube output $\geq 2\text{L}$ within a 24-h period
Type 5	Fatal bleeding
Major Vascular Complication	Access site or access-related vascular injury (dissection, stenosis, perforation, rupture, arteriovenous fistula, pseudoaneurysm, hematoma, irreversible nerve injury, compartment syndrome, percutaneous closure device failure) leading to death, life-threatening or major bleeding, visceral ischemia, or neurological impairment
Pericardial Effusion (PE)	The presence of an abnormal or unexpected amount ( $>10\text{mm}$ ) of fluid or air in the pericardial space identified using echocardiography as echo-free space between the epicardium and parietal pericardium throughout the cardiac cycle. For the purposes of this study, PEs must include one or more of the following: 
 
1) Be accompanied by chest pain or other clinical symptoms (see definition of Cardiac Tamponade)
 
2) Have an increase of <math>>10\text{mm}</math> from baseline in either the width (circumferential) or largest measured dimension (loculated) by echocardiographic imaging
 
3) Require percutaneous or surgical drainage
 
 Pericardial effusions can be further characterized as follows: 
 
- Onset: Acute (intra-procedural), Subacute (post-procedure – 60 days), Long-term (<math>>60</math> days)
 
- Size: Mild (<math>\leq 10\text{mm}</math>), Moderate (11-20mm), Large (<math>>20\text{mm}</math>)
 
- Distribution: Circumferential or Loculated
 
- Hemodynamics: With or without Cardiac Tamponade or Effusive-Constrictive
 
- Type: Transudate, Exudate, Hydropericardium (transudate, plasma ultrafiltrate), Hemopericardium (blood in pericardial space), Chylopericardium (chylous pericardial fluid), Pyopericardium (purulent pericardial effusion), or Pneumopericardium (air in the pericardium)
 

Residual Gap	Space between the implanted device and adjacent LAA tissue. This gap is measured on TEE where there is high velocity color flow and a 2d image showing space between implant and tissue.
Roll-In	WaveCrest subjects enrolled prior to a site’s randomization phase who had vascular access attempted
Stroke/TIA All Stroke	Any ischemic, hemorrhagic, or indeterminate stroke

	Title: The WAVECREST 2 Trial  Clinical Investigational Plan	Doc. #: CHX_IP014	Rev: H
---	--	-----------------------------	------------------

Ischemic Stroke	Sudden onset neurological deficit in a vascular territory thought to be due to cerebral or retinal ischemia that a) lasts longer than 24 hours or b) lasts less than 24 hours and is associated with a neuroanatomically relevant lesion on neuroimaging or confirmed visualized retinal infarct. A global (rather than focal) deficit thought to be due to anoxic brain injury is not considered a stroke. Ischemic stroke with hemorrhagic transformation is also categorized here.
Hemorrhagic Stroke	Any symptomatic intracerebral or subarachnoid hemorrhage.
TIA	Sudden onset neurological deficit in a vascular territory thought to be due to cerebral or retinal ischemia with resolution in less than 24 hours and without evidence of tissue injury on imaging or fundoscopic examination
Major Stroke	
 
Any change on the mRS score > 2 points that persists at 90 days post-stroke
 

Minor Stroke	
 
Stroke symptoms which last longer than 24 hours with evidence of tissue injury but which does not meet definition of Major Stroke
 

Stroke of Cardioembolic Origin	Using ASCOD Classification system  Stroke will be considered cardioembolic except if there is: 
 
Another “potentially causal” mechanism is identified (any of A1, S1, O1, D1)
 

Systemic Thromboembolism	Any peripheral ischemic event evidenced by ischemic tissue or radiologic imaging evidence of perfusion deficit
Vulnerable Population	Individuals whose willingness to volunteer in a clinical trial could be unduly influenced by the expectation, whether justified or not, of benefits associated with participation or of retaliatory response from senior members of a hierarchy in case of refusal to participate Example: individuals with lack of or loss of autonomy due to immaturity or through mental disability, impoverished persons, prison population, and those incapable of giving consent.

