	
 
10. History of symptomatic carotid, intervertebral, or intracranial artery occlusion or stenosis without revascularization with the exception of known occlusion without symptoms > 6 months
 
11. Modified Rankin Scale Score <math>\geq</math> 4
 
12. Chronic resting heart rate > 110 bpm
 
13. Congenital or other clinically significant cardiac anomalies requiring cardiac surgery or interventional repair
 
14. Stroke or transient ischemic attack (confirmed by Neurologist) within 60 days prior to enrollment
 
15. Myocardial infarction within 60 days prior to enrollment
 
16. Sepsis or any active infection requiring oral antibiotic therapy within 14 days or intravenous antibiotic therapy within 30 days prior to enrollment
 
17. Surgical or interventional cardiovascular and non-cardiovascular procedure including cardioversion within 30 days prior to enrollment or AF ablation within 60 days prior to enrollment or any planned general surgery or planned interventional procedure within 90 days after enrollment or any planned cardiac surgery
 
18. On renal replacement therapy, serum creatinine > 3.0 mg/dl (265 <math>\mu</math>mol/L) or calculated creatinine clearance < 25 ml/minute
 
19. Thrombocytopenia (<60,000 platelets/mm^3), leucopenia (white blood cell count < 3,000 cells/mm^3), or anemia (hemoglobin concentration < 10 gram/deciliter)
 
20. Any medical disorder or psychiatric illness that would interfere with successful completion of the trial
 
21. Currently participating in an investigational drug trial or another device trial that has not completed the primary endpoint (trials requiring extended follow-up for products that are commercially available are not considered investigational trials). Concurrent enrollment in the ACC LAAO Registry is permitted.
 
22. Subject belongs to a vulnerable population (see definition in Appendix I: Acronyms and Definitions)
 
23. Any condition that would reduce life expectancy to less than 2 years
 
24. Women of childbearing potential who are, or plan to become pregnant during the time of the trial (method of assessment per physician discretion)
 

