**Descriptive Effectiveness Endpoints**

The following effectiveness endpoints will be descriptively summarized:

 	Title: The WAVECREST 2 Trial  Clinical Investigational Plan	Doc. #: CHX_IP014	Rev: H
--	--	-----------------------------	------------------

- Primary effectiveness event rate at 6 months, 3 years, 4 years and 5 years
- Composite of all stroke, systemic thromboembolism, or TIA at 45 days, 6 months, and at each annual follow-up period
- Landmark analysis of primary effectiveness endpoint from the 45-day visit to the time of each annual follow-up period
- Landmark analysis of the incidence of ischemic stroke from 6 months following device implantation and discontinuation of oral anticoagulant and dual antiplatelet therapy
- Composite of all-cause stroke at 45 days, 6 months, and at each annual follow-up period
- Incidence of thrombus on the surface of the device at 45 days, 1 year, and throughout all follow-up
- Strokes adjudicated as ischemic, hemorrhagic, or indeterminate at 45 days, 6 months, and at each annual follow-up period - see definition in **Appendix I: Acronyms and Definitions**
- Strokes adjudicated as major or minor at 45 days, 6 months, and at each annual follow-up period - see definition in **Appendix I: Acronyms and Definitions**
- Stroke adjudicated as cardioembolic in origin at 45 days, 6 months, and at each annual follow-up period - see definition in **Appendix I: Acronyms and Definitions**
- Freedom from oral anticoagulants after each protocol-required follow-up visit
- Number of devices used per subject
- Procedural success – see definition in **Appendix I: Acronyms and Definitions**
- Technical success – see definition in **Appendix I: Acronyms and Definitions**
- Device success – see definition in **Appendix I: Acronyms and Definitions**
- LAA closure rate at 45 days, 6 months, and 1 year as reported by the ECL– see definition in **Appendix I: Acronyms and Definitions**
- Procedure time, device duration, contrast usage, and fluoroscopy time

 	Title: The WAVECREST 2 Trial Clinical Investigational Plan	Doc. #: CHX_IP014	Rev: H
--	---	-----------------------------	------------------

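### Minor Stroke is not the complement of Major Stroke, so some adjudicated strokes fall in neither class; and the Major threshold, measured from entry, is out of reach for a survivor who entered at mRS 3

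*Protocol*

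**What the plan says.** All the definitions are in Protocol Appendix I.

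- **Major Stroke:** "Any change on the mRS score > 2 points that persists at 90 days post-stroke".
- **Ischemic Stroke:** a sudden deficit that "a) lasts longer than 24 hours or b) lasts less than 24 hours and is associated with a neuroanatomically relevant lesion on neuroimaging", with a visualized retinal infarct as an alternative to the lesion. Branch (a) has no imaging condition.
- **Hemorrhagic Stroke:** "Any symptomatic intracerebral or subarachnoid hemorrhage", with no duration rule.
- **TIA:** resolution within 24 hours and no evidence of tissue injury.
- **Minor Stroke** is worded as follows: "Stroke symptoms which last longer than 24 hours with evidence of tissue injury but which does not meet definition of Major Stroke".

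Protocol Section 4.4.2 (and the Synopsis) excludes an mRS of 4 or more, so a subject may enter at 3. Section 3.7 schedules the mRS at baseline and afterwards only when the stroke questionnaire or a neurology consultation triggers it. Section 6.12 requires a repeat at 90 (± 15) days after any confirmed stroke.

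The two classes feed a descriptive effectiveness endpoint in the Synopsis and Section 15.6: "Strokes adjudicated as major or minor at 45 days, 6 months, and at each annual follow-up period". Section 15.6 refers to Appendix I for the definitions. SAP Section 8.7.2 estimates a rate per subject-year for each class, and SAP Section 8.7 adds 95% confidence intervals and descriptive p-values between arms.

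**The concern.** A severity split is useful only if every stroke lands in exactly one class. Here Minor carries two conditions of its own, duration and tissue injury, that the stroke definitions do not impose together. A short deficit with a lesion is a clear example. Appendix I makes it a stroke and not a TIA, yet it cannot be Minor.

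The Major rule has a different problem. It is a fixed step on a bounded scale, and eligibility lets subjects start high on that scale. Entry at mRS 2 or 3 is plausible: prior stroke alone scores 2 on CHADS2 and meets the risk-score criterion, and only a stroke or TIA in the last 60 days is excluded.

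At stake is one comparative table. Readers will look at it, because Protocol Section 2.6 cites a 49% lower risk of disabling stroke relative to warfarin among the control device's results. As written, the table could fail to add up, and a severely disabling stroke could appear as minor or not appear at all.

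**Working it through.** The plan gives no figure to reproduce, so the check applies the written rules literally to every case.

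**Inputs.** The Appendix I definitions and the entry limit of mRS 3 (Section 4.4.2). Two assumptions are needed. First, the living mRS grades run 0 to 5, since Appendix IV only links to the scale; death is tried both as grade 6 and as no grade. Second, a hemorrhage counts as tissue injury.

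**Step 1: coverage when the mRS change is 2 or less (not Major).** Minor = (over 24 h) AND (tissue injury) AND (not Major).

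| Type | Duration | Tissue evidence | Is it a stroke? | Class |
|---|---|---|---|---|
| Ischemic | > 24 h | yes | yes | Minor |
| Ischemic | > 24 h | no | yes, branch (a) | neither |
| Ischemic | < 24 h | yes | yes, branch (b) | neither |
| Ischemic | < 24 h | no | no (TIA) | not applicable |
| Hemorrhagic | > 24 h | yes | yes | Minor |
| Hemorrhagic | < 24 h | yes | yes | neither |

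Three kinds of adjudicated stroke have no class. With a change of 3 or more, every stroke in the table is Major, whatever its duration or imaging. The gap therefore removes only non-major strokes.

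**Step 2: reach of the Major rule.** A change of more than 2 on a whole-number scale means at least 3. Lowest qualifying grade = entry grade + 3.

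| Entry mRS | Lowest qualifying grade | Qualifying grades among survivors |
|---|---|---|
| 0 | 0 + 3 = 3 | 3, 4, 5 |
| 1 | 1 + 3 = 4 | 4, 5 |
| 2 | 2 + 3 = 5 | 5 |
| 3 | 3 + 3 = 6 | none |

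From entry 3, only death scored as 6 qualifies. If the scale has no death grade, nothing does. The result for survivors is the same either way. A lasting move from 3 to 5 is a change of 2, so it is Minor if symptoms exceeded 24 hours with tissue injury, and otherwise unclassified.

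**Step 3: what the Major wording leaves open.** It names neither a direction nor a reference score. Read literally, an improvement from 3 to 0 is a change of 3 and qualifies. If the reference is the last score before the stroke, a subject who had improved from 3 to 2 reaches Major at 5 (5 − 2 = 3). The visible text also has no rule for death before day 90 or for a missing 90-day score.

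**Step 4: direction of each effect.** The ceiling in Step 2 moves severe strokes out of Major. The gap in Step 1 does not change the Major count, and it raises the Major share of classified strokes. As an illustration with assumed figures, if 25% of all strokes were Major and 20% were unclassified, Major would be 0.25 / (1 − 0.20) = 31% of classified strokes. The two defects do not push the same way.

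**The case against.** The strongest reply is that little depends on this split. It is one descriptive endpoint, and SAP Section 8.7 seeks no labeling from it. Every affected stroke still counts in the all-stroke and the ischemic/hemorrhagic/indeterminate summaries, and ischemic ones count in the primary effectiveness endpoint. The 90-day mRS is collected after any confirmed stroke, so severity could be tabulated directly. Section 6.12 requires brain imaging at an unscheduled neurology visit unless adequate recent imaging exists, so few strokes should lack tissue evidence merely because nobody looked. All of this stands, and it limits the importance of the point. Routine imaging does not close the gap, however, because it also finds the short deficits with a lesion that Minor cannot hold.

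A second reply is that the adjudication committee will cope. Its charter is not available and parts of the SAP are blacked out, so a supplementary rule cannot be excluded. But Section 15.6 refers to Appendix I, and a rule elsewhere that filled the gap would have to be reconciled with that text.

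A third reply is that it is too absolute to say a subject entering at 3 can never have a non-fatal major stroke. That is right. The statement depends on measuring from entry, which the text does not say. Because the mRS is routine only at baseline, the entry score is the one reference sure to exist, so that reading is reasonable but not certain.

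**Conclusion.** The definitions are wrong as written, with effects limited to the descriptive major/minor endpoint. Three kinds of non-major stroke have no class, so major plus minor need not equal all strokes. Measured from entry, and assuming living grades 0 to 5, a survivor who entered at mRS 3 cannot have a major stroke, and one who entered at 2 qualifies only at grade 5.

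A reader might infer that both defects cause severity to be under-reported. Only the mRS ceiling does so; the coverage gap leaves the Major count unchanged. A reader might also infer that disabling strokes in already disabled subjects will all be labelled minor. Some would instead be unclassified, depending on duration and tissue evidence. Nor do the documents support any effect on the primary endpoint.

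The size cannot be given. The documents state neither the distribution of entry mRS nor the mix of stroke types. A count of primary events would be the wrong denominator in any case, since it includes systemic embolism and omits hemorrhagic and indeterminate strokes. This is a minor point, but it is cheap to correct.

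**What to change.** 1. Define Minor Stroke as any CEC-adjudicated stroke that does not meet the Major Stroke definition. This alone closes the coverage gap and makes the table add up.
2. State in Major Stroke that the mRS change is a worsening, and name the score from which it is measured.
3. Have the sponsor reconcile the threshold of more than 2 points with the entry limit of mRS 3, and state how death before day 90 is classed. The documents offer no basis for preferring a particular threshold or grade, so that choice is the sponsor's.
4. Carry the same wording into the CEC Charter and the SAP.

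The cost is wording in Appendix I, the charter and the SAP. It needs no new visits, data or subjects. It should be settled before adjudicated data are unblinded.
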